6 STUDY INTERVENTIONS/INVESTIGATIONAL PRODUCTS

6.1 Study Product Description – Hypertonic Saline

6.1.1 Acquisition

Hypertonic saline (HPS) (3%) will be obtained in the United States and shipped to Blantyre.

6.1.2 Formulation, Packaging, and Labeling

Product is packaged in 500ml bags. Storage is recommended at room temperature (25°C).

6.1.3 Product Storage and Stability

Bags of HS will be stored in a cabinet in the PRW pharmacy adjacent to the ward. It will be protected from direct light. The pharmacy is equipped with an air conditioning unit and is provided with back up electricity by a diesel operated generator in case of power outages. Minimum and maximum ambient temperatures will be recorded daily.

6.2 Dosage, Preparation and Administration of Study Intervention (HPS)^{250, 251}

HPS will be administered through a cannula placed in a large peripheral vein. All participants will already have a peripheral cannula in place for maintenance fluid replacement. Dosage and adjustments in infusion rates will be administered per Standard Operating Procedures.

The HPS saline bag will be connected to a volumetric infusion set. Based on the weight of the subject, and the current sodium concentration, the appropriate amount of HPS will be placed in the chamber and the tubing attached to the secondary port of the intravenous line already in use for delivery of maintenance fluids. Only the amount of fluid to be installed in the current intervention will be delivered to the chamber, to avoid the possibility of overdose.

The HPS loading dose will take place over a 30-minute period, with duration regulated by adjustment of the drop rate. Maintenance fluids will continue during the infusion of the HPS loading dose to minimize the possibility of phlebitis.

After the loading dose is complete, the infusion rate will be reduced to the maintenance infusion rate (see Standard Operating Procedure).

6.3 Modification of Study Intervention for a Participant (HPS)

Although sodium abnormalities are rare in CM, in the event that a participant has a (Na⁺) level of > 150 mmol/L on admission, the initial bolus will be deferred and the sliding scale dosing detailed in Table 3 will instead be followed.

The subsequent dosing of HPS is planned on a sliding scale, with the goal of maintaining serum sodium levels between 150 and 160 mmol/L. Serum sodium levels will be checked every 3 hours for the first 12 hours of the study, and then every six hours, unless designated otherwise (Table 3).

Table 5. Dosing schedule for hypertonic saline

Serum Sodium	Dose of 3% HPS	Sodium recheck
< 145 mmol/L	5 mL/kg (bolus)*	3 hours
145 – 150 mmol/L	2 mL/kg (bolus)*	3 hours
150 - 160 mmol/L	None	6 hours
>160 mmol/L	Hold infusion until serum sodium is ≤ 155, restart at 0.5 mL/kg/hr	1 hour

*If > 3 boluses are required to maintain serum sodium between 150-160, then increase infusion by 0.25 mL/kg until no further boluses are required.

Further modifications to the HPS dose will be made in the event of the following laboratory abnormalities (electrolyte abnormality grading detailed in Appendix B):

- Grade 4 hypokalemia (see Toxicity Table in Appendix B)
- A pH drop of more than 0.2 within 6 hours
- Chloride > 125 mmol/L
- Serum osmolality > 340 mOsm

In these instances, planned HPS doses will be held, and corrective actions (detailed in Section 9.2.4) will be taken. Electrolytes will be rechecked in 3 hours and the normal dosing schedule will be reinstated if electrolytes are no longer in the Grade 4 toxicity range.

If the pH < 7.25 or falls by 0.2 within 6 hours or if the serum chloride is > 125 mmol/L, the 3% saline infusion will be stopped and converted to a 1:1 ratio of 3% sodium chloride/sodium acetate solution.

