2.2 Agent(s)/Intervention(s)

The goal of this clinical trial is to compare outcomes in children treated with the current standard of care (antimalarial drugs and elevation of the head of the bed 30 degrees) to outcomes in children randomized to receive one of two different approaches to ameliorating the effects of increased brain volume:

- Arm 1: Usual care + immediate mechanical ventilatory support during the initial high risk period, with ventilator withdrawal once brain volume has decreased (brain volume score ≤ 5), and the patient has improved clinically (Blantyre Coma Score ≥ 3).

- Arm 2: Usual care + intravenous hypertonic saline, withdrawn once brain volume has decreased (brain volume score ≤ 5) and the patient has improved clinically (Blantyre Coma Score ≥ 3).
- Arm 3: Usual care (antimalarial drugs plus elevation of the head of the bed by 30 degrees)

Background

The study design was informed by (a) the strong association between increased brain volume and a fatal outcome in pediatric CM, (b) the rapid reversibility of increased brain volume in CM survivors, and (c) the importance of identifying the most feasible intervention for use in malaria-endemic settings.

One challenge is that direct monitoring of intracranial pressure (via intraventricular catheters, or subarachnoid or intraparenchymal bolts) in this setting is relatively contra-indicated --- the risk of infection is too high⁸². Indirect measurements of brain volume are required; the data to date have been derived via MRI. Though the MRI findings are useful and reliable, they are not scalable across sub-Saharan Africa. Consequently, efforts to identify more user-friendly approaches to identifying patients with severely increased brain volume will be evaluated at the same time as this clinical trial is conducted.

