 - Continuous monitoring of heart rate and rhythm from EKG, respiratory rate, and pulse oximetry via monitor, and blood pressure via arterial line or cuff. Signals will be archived for offline analyses aimed at identifying heart rate variability patterns over time associated with CM and with clinical improvement or decline in association with treatment.

- Electrolytes and acid-base balance 3-hourly during the first 24 hours and 6-hourly thereafter (in those randomized to hypertonic saline)
- PRW and PICU
 - 2-hourly assessments of vital signs (including temperature) and Blantyre Coma Score until BCS = 5 and temperature is $\leq 37.5^{\circ}\text{C}$ for 24 hours, then 6-hourly.
 - 6-hourly assessments of malaria parasitemia and hematocrit, until two consecutive parasitemia counts are negative.
 - 12-hourly neurological examinations,
 - Daily ophthalmoscopy while unconscious
 - Daily ONSD measurements (while unconscious)
 - Daily TCD examinations
 - Daily MRI examinations (while unconscious if participant is clinically stable for transportation to undergo neuroimaging)

The primary objective (treatment success or failure) will be determined within the first 7 days of hospitalization (Figure 8)

Secondary objectives (Figure 8)

1. The secondary objective involving neurological sequelae at 1, 6, and 12 months after randomization will be determined in survivors randomized in the clinical trial.
2. The secondary objective of identifying surrogate measures of increased brain volume will include participants in the clinical trial as well as study subjects who are screened but do not meet inclusion criteria for clinical trial enrollment e.g. their brain volume is not increased enough to qualify for enrollment in the trial and are therefore not randomized.
3. The secondary objective of assessing the safety of early intubation and mechanical ventilation will include participants in the clinical trial as well as study subjects with CM who are screened but do not meet inclusion criteria for clinical trial enrollment e.g. their brain volume is not increased enough to qualify for enrollment in the trial and are therefore not randomized.
4. TCD endpoints will be determined on all participants (see section 7.2.2.4)]

Choice of participant population and sample size considerations

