1. Arm 1: Usual care + immediate mechanical ventilatory support (VENT) for a maximum of 7 days, with ventilator withdrawal once brain volume has decreased (brain volume score ≤ 5) or the patient has improved clinically (modified Blantyre Coma Score ≥ 3) or the patient dies or meets criteria for severe irreversible neurologic failure.
2. Arm 2: Usual care + intravenous hypertonic saline (HPS) for a maximum of 7 days, withdrawn once brain volume has decreased (brain volume score ≤ 5) and the patient

has improved clinically (Blantyre Coma Score ≥ 3) or the patient dies or meets criteria for severe irreversible neurologic failure.

3. Arm 3: Usual care (UC); intravenous fluids, intravenous artesunate; antipyretics, anticonvulsants and blood transfusions as needed; nutritional support) for a maximum of 7 days, or until brain volume has decreased (brain volume score ≤ 5) and the patient has improved clinically (Blantyre Coma Score ≥ 3) or the patient dies or meets criteria for severe irreversible neurologic failures

Participants will remain in the study throughout their hospitalization and, in survivors, through the 12-month post-randomization follow-up visit. Children are discharged when two sequential 6-hourly blood films are free of malaria parasites, when they have been afebrile for 24 consecutive hours, and when they are able to take medications and food by mouth. Final data collection will be at 12 months post-randomization.

Stratification:

No stratification is required. The ages of retinopathy-positive CM with severely increased brain volume per MRI who survived were compared to those of participants from the same population that died. There was no difference in the age structure (data not shown, $p=0.95$).

Primary and secondary outcomes.

The primary outcome is treatment success or failure, determined within the first 7 days. Treatment success is recovery. Treatment failure is death, ventilatory rescue (for participants in Arms 2 and 3) or meeting criteria for severe irreversible neurologic failure.

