- Arm 1: Usual care + immediate ventilatory support for a maximum of 7 days. These subjects will undergo rapid sequence intubation and be placed on a mechanical ventilator to maintain physiological pCO_2 levels for a maximum of 7 days. Arterial blood gas determinations will take place every 3 hours for the first 24 hours, then every 6 hours until the participant is extubated. Non-scheduled blood gas determinations may occur at the discretion of the PICU physician. Participants will remain in the Pediatric ICU during mechanical ventilation and after its discontinuance.
- Arm 2: Usual care + infusion of 3% hypertonic saline to achieve a target blood concentration of 150-160 mmol/L. Participants will remain in the Pediatric ICU during hypertonic saline infusion. Participants randomized to hypertonic saline administration will have electrolytes evaluated on admission and every six hours thereafter until they regain consciousness ($\text{BCS} \geq 3$)
- Arm 3: Usual care (elevation of the head of the bed 30 degrees and intravenous antimalarial drugs).

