Lactate levels will be determined on admission and every six hours thereafter until the participant has maintained a BCS of 3 for greater than 4 hours. Testing is done with a point of care testing machine. This test uses one drop of blood obtained by finger prick. The monitor will be tested for accuracy on manufacturer supplied test strips every morning.

HIV testing will be performed on all participants, subject to permission being granted by the parent/ guardian present. The test will be performed after recovery of the participant is anticipated by the clinical staff unless test results are thought to have relevance for acute clinical care. Two rapid tests will be performed on a blood sample obtained by finger prick. In the event of discordant results an HIV polymerase chain reaction test will be performed.

Full Blood Count: Participants will have blood drawn for a full blood count (FBC) on admission. FBC includes hemoglobin, hematocrit, RBC indices, white blood cell (WBC) with 5-part differential, and platelet count.

Electrolytes: Participants enrolled in the study who are randomized to hypertonic saline administration will have electrolytes evaluated on admission and every six hours thereafter until they regain consciousness. As this is a crucial measurement in the appropriate administration of the investigational product, a back-up machine will be available.

Respiratory infection screening: On admission, two nasopharyngeal swabs: one for viral identification and one for bacterial detection and quantification by real time PCR. For viral identification we will use the respiratory PCR panel (FilmArray) which includes simultaneous detection of 18 viruses (adenovirus, 4 endemic coronaviruses, SARS-CoV-2, hmpv, RSV, 5 influenza viruses, rhinovirus/enterovirus and 4 parainfluenza viruses). Individual bacterial real time PCR analysis and quantitation will be performed for *Staphylococcus aureus*, *Streptococcus pneumoniae*, *Haemophilus influenzae*, and *Moraxella catarrhalis*.

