Appendix A

Schedule of Events

Clinical and Laboratory Evaluations

A = performed on all children on PRW/PICU [(A) = only if still unconscious]

S = performed on children eligible to be screened for TBS study

I = performed as part of TBS trial [(I) = only if still unconscious]

Event	Admission	Screening	With TBS consent	Day 1	Day 2	Days 3 -7	Follow-up visits
History	A						A
Physical Exam	A			A,A	A,A	A,A	A
Vital signs	A			A – q2 hours	A – q2 hours	A – q2 hours	A
IV anti-malarial Rx	A			A,A	A,A		
PO anti-malarial Rx						A (3 day course)	
MP and PCV	A			A A A A	(A)(A) (A)(A)	(A)(A) (A)(A)	A
Lactate and glucose check	A			A A A A	(A)(A) (A)(A)	(A)(A) (A)(A)	
Lumbar Puncture	A						
Retinal exam		S		(I,)	(I,)	(I,)	
MRI		S		I	(I)	(I)	I (1 month)
NIRS		S		I	I	I	I (1 month)
TCD		?	I?	I	I	I	I (1 month)
ONSD			I	I,	(I,)	(I,)	I
Expanded neurologic exam			I	I, I	(I,I)	(I,I)	I
Heart rate variability			I	I	I	I	
Lung ultrasound			I	I	I	I	
Brain swelling intervention			I	I	I	I	

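### HPS arm: opposite dose instructions at Grade 4 hypokalemia, and routine electrolyte schedules that disagree on interval and end point

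*Combined protocol and SAP*

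**What the plan says.** **Grade 4 hypokalemia.** Section 6.3 lists it among the laboratory findings at which planned HPS doses are withheld, and sends the reader to section 9.2.4 for the corrective action. Section 9.2.4.2 takes the same event (potassium below 2.0 mmol/L, as in Appendix B), adds potassium to the maintenance fluid, and has HPS boluses carry on with 3-hourly electrolytes.

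**Routine checks.** There are three schedules.
- Section 4, PICU monitoring: "Electrolytes and acid-base balance 3-hourly during the first 24 hours and 6-hourly thereafter (in those randomized to hypertonic saline".
- Section 6.3: "Serum sodium levels will be checked every 3 hours for the first 12 hours of the study, and then every six hours, unless designated otherwise". The exception points to the dosing table (Table 5), which sets sodium rechecks at 3 hours below 150 mmol/L, 6 hours at 150 to 160, and 1 hour above 160.
- Section 8.1: "Participants randomized to hypertonic saline administration will have electrolytes evaluated on admission and every six hours thereafter until they regain consciousness", with consciousness taken as a Blantyre Coma Score (BCS) of 3 or more. Section 8.2.1 repeats this rule.

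**When HPS stops.** Section 2.2 has "intravenous hypertonic saline, withdrawn once brain volume has decreased" and section 4 has "intravenous hypertonic saline (HPS) for a maximum of 7 days, withdrawn once brain volume has decreased". In both places this means a brain volume score of 5 or less together with a BCS of 3 or more. Section 2.3 gives the same joint rule.

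**MRI after waking.** Section 4 schedules "Daily MRI examinations (while unconscious if participant is clinically stable for transportation to undergo neuroimaging", and the Appendix A legend for the bracketed entries after day 1 reads "I = performed as part of TBS trial [(I) = only if still unconscious". Table 8 in section 11.5 lists MRI at admission and then daily, with no such limit.

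**The concern.** HPS is titrated to these results, and section 2.4.1.2 names hypernatremia and hypokalemia as direct consequences of the treatment. At potassium below 2.0 mmol/L the protocol tells staff both to withhold HPS and to go on giving it. Sections 6.5 and 15.6 treat irregular administration and any noncompliance as deviations, so whichever action the nurse takes breaches one section.

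The monitoring text raises a second problem. Staff who work from section 8 take half as many routine samples on day 1 as section 4 asks for. They may also stop sampling at a BCS of 3 while HPS continues because the brain volume score is still 6 or more. Section 2.4.1.2 rests its safety argument on close monitoring described in section 9.2.4, but that section gives no routine interval. At stake is the safety of the children on HPS, not the trial's inference.

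**Working it through.** **1. The hypokalemia instructions side by side**

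| | Section 6.3 | Section 9.2.4.2 |
|---|---|---|
| Trigger | Grade 4 hypokalemia | Potassium below 2.0 mmol/L (Grade 4) |
| HPS | Planned doses withheld | Boluses go on |
| Afterwards | Recheck at 3 h; resume when no longer Grade 4 | 3-hourly checks until below Grade 3 |

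The words doses and boluses do not separate the two rules. The dose column of Table 5 consists largely of boluses (5 mL/kg below 145 mmol/L, 2 mL/kg at 145 to 150), so a bolus is a planned dose.

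**2. Routine post-baseline checks in the first 24 h, child on target**
- Section 4: 24/3 = 8.
- Section 6.3: 12/3 + 12/6 = 6, or 24/6 = 4 if Table 5's 6 h interval replaces the 3 h rule.
- Section 8: 24/6 = 4.

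Over a full 7 days with no early end, the three default schedules give 32, 30 and 28. After 24 h all are 6-hourly, so the difference in interval is confined to day 1.

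**3. End points**
- Section 8: BCS of 3 or more.
- HPS withdrawal: score of 5 or less and BCS of 3 or more, at most 7 days.
- Section 4 and Table 5: no end at waking.

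A child with BCS of 3 or more and a score of 6 or more is past section 8's end point but still on HPS. Under section 8 alone, 24/6 = 4 electrolyte checks per day then fall away. Under section 6.3 the sodium rechecks continue, but Table 5 names sodium only. First detection of chloride above 125 mmol/L, osmolality above 340 mOsm or Grade 4 potassium (all hold triggers in section 6.3) therefore rests on routine electrolyte sampling, unless a full panel is run with each sodium, which the protocol does not say.

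**4. What an extra 3 h means for sodium on day 1**

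Assumptions, not in the documents unless noted: 3% saline is 30/58.44 = 0.513 mol/L, or 513 mmol/L; body water 0.55 to 0.70 L/kg; starting sodium 155 mmol/L; no loss of sodium or free water; rate 0.5 mL/kg/h (the Table 5 restart rate) to 1.0 mL/kg/h (assumed, since the dosing SOP is not available). With V the volume infused in L/kg and W body water, the rise is V × (513 − 155)/(W + V).
- 3 h, low: 0.0015 × 358/0.7015 = 0.8 mmol/L.
- 3 h, high: 0.003 × 358/0.553 = 1.9 mmol/L.
- 6 h, low: 0.003 × 358/0.703 = 1.5 mmol/L.
- 6 h, high: 0.006 × 358/0.556 = 3.9 mmol/L.

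A child at 160 mmol/L would reach at most about 160 + 3.9 = 163.9, below the Grade 1 threshold of 166 in Appendix B. Ignoring the infused water altogether gives 0.006 × 513/0.55 = 5.6 over 6 h, or 165.6, still below 166.

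**5. Children a correction can reach**

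The projected enrollment table in section 4 has 14 HPS children in 2022 and 15 in 2023, so 29. If the 2022 season is already complete, 15 remain. Against section 8, extra day-1 samples are at most (8 − 4) × 15 = 60 to (8 − 4) × 29 = 116.

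**The case against.** The schedules can be read as minimums. A team that follows section 4 satisfies sections 6.3 and 8 on day 1. Table 5 tightens checks for any off-target sodium, and 6 hours is its own choice for a child in range. Section 8 does not forbid sampling after waking, and section 2.3 says that swelling in survivors usually settles within 48 hours, so most gaps would be short. Children on HPS stay in the PICU during the infusion (section 8.1), with one-to-one nursing (section 2.4.2), and SOPs that are not part of these documents govern dosage and rate changes (section 6.2).

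Much of this stands. It shows that the practical harm from the schedule conflict is probably small. It does not settle which schedule staff must follow, or when non-sodium checks end. It does not touch the hypokalemia conflict, where no single action satisfies both sections.

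A reader might infer that a child who wakes on HPS has no further sodium check and no scheduled MRI. The documents do not support that. Every row of Table 5 sets a sodium recheck with no end at waking, and section 4 has no such end either. Table 8 lists daily MRI, and section 8.3.2 expects serial scans to bear on HPS withdrawal. The MRI text is inconsistent; it does not establish that no scan is done.

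**Conclusion.** The concern holds as a safety-drafting inconsistency that should be fixed. The firmest part is the pair of opposite dose instructions at potassium below 2.0 mmol/L, which rests on text alone. Next is the disagreement among routine schedules: 8, 6 (or 4) and 4 checks on day 1. The lapse after waking is conditional: it arises only if section 8 is followed, and it then concerns potassium, chloride and other electrolytes, since sodium rechecks continue under Table 5. The documents do not say how often a child wakes with a score of 6 or more, so no total of missed checks can be given.

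The day-1 sodium effect is small: about 0.8 to 1.9 mmol/L for the extra 3 hours, on the assumed rates and body water. A reader might infer that the looser schedule could carry an on-target child into graded hypernatremia; the calculation does not show that. Nor does the point alter any endpoint, power, alpha, analysis or between-arm comparison.

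**What to change.** 1. Amend section 9.2.4.2 so that HPS doses, boluses included, are held at Grade 4 hypokalemia as in section 6.3, and give one criterion for resuming.
2. Put section 4's schedule (electrolytes and acid-base 3-hourly for 24 h, then 6-hourly) into sections 4, 6.3, 8.1 and 8.2.1 as the single minimum, continued until HPS is stopped. State that Table 5 and section 9.2.4 rechecks take precedence whenever they are shorter.
3. Say whether MRI is repeated in a child who wakes on HPS with a last score of 6 or more, and align section 4, Appendix A and Table 8.
4. Editorial: correct the four Table 3 citations (two in section 6.3, two in section 9.2.4.1) to Table 5, correct the section 6.1.5 pointer to 6.3, and add an electrolyte row to Appendix A.

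The cost is a wording amendment. It adds no routine day-1 sample beyond what section 4 already asks for. Measured against section 8 it adds at most 4 per child on day 1 (60 to 116 in all), plus 4 per day for any time that HPS runs after waking. The bedside analyser (section 2.3) and a back-up machine (section 8.2.1) are already planned.

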2.4.1.2 Hypertonic saline

The known side-effects of hypertonic saline include:

- Hypernatremia
- Hypokalemia
- Rebound cerebral edema upon termination of therapy

These conditions are all a direct result of the increased sodium and osmolarity that are also the goal of the intervention. Assiduous monitoring of electrolytes (as described in 9.2.4) will therefore be undertaken to balance desired effects with possible side effects.

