Variable	OS mean	OS SD	TBS mean	TBS SD	P value
Age (months)	48.25	27.54	59.63	27.88	0.168
Glucose	5.87	2.94	5.63	3.13	0.914 ^d
Hematocrit (%)	23.36 ^a	6.29	25.54	6.97	0.555 ^d
Platelets (*1000/MicroL)	148.9 ^b	373.7	94.3 ^c	176.2	0.993 ^d

OS= observational study (n=48), SD= standard deviation, TBS= treating brain swelling clinical trial (n=16)

^a n=45, ^b n=47, ^c n=15. ^d nonparametric test.

There was no significant difference in admission Blantyre Coma score (p=0.948), sex (p=0.885) or outcome (death/survival, p=0.551) between the 48 children in the observational study and the 16 randomized participants in the Treating Brain Swelling clinical trial.

We therefore conclude that participants enrolled in the observational study (n=48) are comparable to participants randomized to Usual Care (n=16) in the Treating Brain Swelling clinical trial.

We anticipate enrollment in the Usual Care arm in the 2023 season (see below) at a reduced ratio compared to the intervention arms.

Possible future declaration of futility of the ventilation arm:

If we combine the mortality risk in Historical Controls and participants already randomized to Usual Care, the mortality risk of the combined historical control group and children randomized to Usual Care is 36%. At the end of the 2021 season, the mortality risk in the VENT arm was 26.3%. (Five of 19 participants randomized to VENT died or were brain dead.) With only these data, the test of the null hypothesis of a null difference in mortality is not significant (p-value 0.818, 2-sided test).

We believe it likely that VENT will, in the future, be declared futile. If so, randomization of participants enrolled in the Treating Brain Swelling clinical trial after the declaration of futility of VENT would be to HPS or UC. A formal approach to futility assessment for VENT is provided below.

Table 4. Projected enrollment

	2018 – 2021	2022	2023	Total
*Usual care (UC)	64	0	4	68
Ventilatory support (VENT)	19	7	6	32
Hypertonic saline (HPS)	3	14	15	32

*historical controls + study participants enrolled in 2018 and 2019.

Assuming that enrollment in 2023 follows the same trend seen since the beginning of the clinical trial, we will be able to detect a 50% or more risk reduction in either the VENT or HPS arms, compared to UC.

Choice of interventions

The three study arms of the study will be:

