9.2.4.2 Hypokalemia

As per the toxicity table attached as Appendix B, a serum potassium measurement of <2.0 mmol/L will be defined as a Grade 4 adverse event. Corrective action will be in the form of adding 40 mmol/L of KCl to the maintenance IV fluids (an increase from the 17mmol/L K⁺ present in ½ Strength Darrow’s). IV fluid infusion rate will remain the same. HPS boluses will continue, and electrolytes will be monitored at 3 hour intervals until K⁺ returns to below Grade 3 disturbances.

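### For Grade 4 hypokalemia, Section 6.3 holds hypertonic saline doses while Section 9.2.4.2 continues the boluses

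*Combined protocol and SAP*

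**What the plan says.** Section 6.3 lists four laboratory findings that change HPS dosing. The first is Grade 4 hypokalemia, graded by Appendix B. For all four it says: "In these instances, planned HPS doses will be held, and corrective actions (detailed in Section 9.2.4) will be taken". After a 3-hour recheck, "the normal dosing schedule will be reinstated if electrolytes are no longer in the Grade 4 toxicity range".

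Section 9.2.4.2 takes up the same finding. It says that a potassium below 2.0 "mmol/L will be defined as a Grade 4 adverse event", adds potassium chloride to the maintenance fluid, and then states: "HPS boluses will continue, and electrolytes will be monitored at 3 hour intervals until" potassium "returns to below Grade 3 disturbances".

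Two other places matter. Section 2.4.1.2 lists hypokalemia among the known HPS side effects and says of that list: "These conditions are all a direct result of the increased sodium and osmolarity that are also the goal of the intervention". Section 6.2 sends the detail elsewhere: "Dosage and adjustments in infusion rates will be administered per Standard Operating Procedures". Those procedures are not part of the documents.

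On the separate minor item, Sections 2.2, 2.3, 4 and 6.7 each state when recovery allows the experimental treatment, including ventilation, to stop. Section 8.3.2 removes children incorrectly withdrawn because of discrepant serial MRI reads from the per-protocol analyses.

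**The concern.** A clinician who sees a potassium below 2.0 mmol/L reads in 6.3 that HPS is held, follows the cross-reference for the corrective action, and finds there that boluses go on. Both are dosing orders at the highest toxicity grade, for a side effect that the protocol attributes to what HPS is meant to achieve. Section 6.5 makes irregular HPS administration a reportable deviation, so either action could be logged as a breach of the other section.

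The stake is patient safety and clean conduct in the HPS arm. It is not the statistical design: no sample size, power, alpha or intention-to-treat result depends on it. The ventilator item has a small analytic side, because the per-protocol exclusion in 8.3.2 needs one agreed rule to judge whether a withdrawal was incorrect.

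**Working it through.** The plan gives no figure to reproduce. The check sets the sections side by side.

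**1. Is it the same event?** Section 6.3 uses Grade 4 by Appendix B, which is below 2.0 mEq/L. Section 9.2.4.2 uses below 2.0 mmol/L and calls it Grade 4. Potassium is monovalent, so the units agree. The trigger is identical.

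**2. Is it the same action?** Section 6.3 holds planned doses. Table 5 lists the boluses in its dose column, so a bolus is a planned dose.

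**3. When do the orders collide?** Only when a bolus is due. Volume = dose × weight. The documents give no weights, so 10 to 20 kg is an assumption.

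| Sodium (mmol/L) | Bolus under 9.2.4.2 | Bolus under 6.3 | Volume at 10–20 kg, 9.2.4.2 vs 6.3 |
|---|---|---|---|
| below 145 | 5 mL/kg | 0 | 5×10 = 50 to 5×20 = 100 mL vs 0 |
| 145–150 | 2 mL/kg | 0 | 2×10 = 20 to 2×20 = 40 mL vs 0 |
| above 150 | 0 | 0 | 0 vs 0 |

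The table covers boluses only.

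**4. Do the end rules conflict?** No. Section 6.3 restarts dosing once potassium leaves Grade 4, at 2.0 or above. Section 9.2.4.2 keeps 3-hourly monitoring until potassium is below Grade 3, which by Appendix B (Grade 3 is 2.0 to 2.4) means above 2.4. One rule governs dosing and the other monitoring, so both can be followed.

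**5. Is the continuous infusion held?** Neither section says so outright. Table 5 puts its infusion instruction (sodium above 160) in the same dose column, which suggests that the hold covers the infusion. But 6.3 speaks of stopping the infusion by name only for low or falling pH and high chloride, which suggests that it is handled separately. The text leaves this open.

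**6. Separate minor item: recovery criterion for ventilator withdrawal.**

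| Section | Criterion |
|---|---|
| 2.2, 2.3 | brain volume score ≤5 AND Blantyre score ≥3 |
| 4 (Arm 1) | score ≤5 OR modified Blantyre score ≥3 |
| 6.7 | decreased to score ≤6 AND modified score ≥3; or modified score ≥4 without repeat MRI |

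Two examples show that no two versions are equivalent. They assume a child randomized at score 7 and treat the Blantyre and modified scores as equal (the verbal item in fact differs). At score 5 with coma score 2, only Section 4 withdraws. At score 7 with coma score 4, Sections 4 and 6.7 withdraw and Sections 2.2/2.3 do not. The 7-day cap, death and irreversible neurologic failure are not recovery criteria and are left out.

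**The case against.** The best defense is that Section 6.2 refers dosing to procedures outside the documents, and one clear bedside instruction may exist there. That stands as a limit on the consequence: inconsistent bedside practice is not shown. It does not repair the text, since any single procedure would still contradict one protocol section.

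Three harmonizing readings fail:
- That doses in 6.3 means only the infusion: Table 5 lists boluses as doses.
- That 9.2.4.2 is about milder hypokalemia: Grade 4 is the only trigger it names, and Grade 3 appears only as the end of monitoring.
- That 9.2.4.2 describes what follows a hold: it mentions neither a hold nor a restart.

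A reader might also infer more than the documents support:
- **A second conflict over end points.** Step 4 shows that the two rules are compatible.
- **That most of the HPS arm is at risk.** The table headed "Table 4. Projected enrollment" places 14 + 15 = 29 of 32 HPS children in 2022 and 2023. That counts children still to be enrolled, not children with potassium below 2.0 and sodium below 150. No frequency is given.
- **That the ventilator versions disagree in a large share of cases.** Counting score combinations says nothing about how many children fall in them, and the pattern depends on the entry score. Section 6.7 is the administration section and the natural operative rule. In Section 4, Arms 2 and 3 join the two conditions with and, so the or in Arm 1 may be a drafting slip.

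**Conclusion.** The contradiction is certain on the text: for potassium below 2.0 mmol/L the protocol both holds and continues HPS boluses. It takes effect when sodium is below 150 mmol/L, with 5 or 2 mL/kg at stake against none (50–100 mL or 20–40 mL at the assumed 10 to 20 kg). How often this arises, and what staff would actually do, cannot be determined from the documents. It must be fixed because it is a safety order at the top toxicity grade and the correction costs almost nothing. The three ventilator-withdrawal versions are a separate, minor inconsistency, relevant to treatment conduct and to the per-protocol set only.

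**What to change.** Amend 9.2.4.2 along these lines:

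> If potassium is below 2.0 mmol/L, hold HPS boluses as in Section 6.3, add KCl to the maintenance fluids, and recheck electrolytes every 3 hours. Restart per the dosing table when potassium is 2.0 mmol/L or above. Continue 3-hourly monitoring until potassium is above 2.4 mmol/L. The continuous infusion is [also held / not held].

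The clinical team fills in the bracket. If it intends boluses to continue, the alternative is to take hypokalemia off the 6.3 hold list. Either way, check the Standard Operating Procedure against the chosen text.

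Minor item: make 6.7 the single recovery rule for ventilator withdrawal, cite it in 2.2, 2.3 and 4, and use it for the 8.3.2 per-protocol exclusion. Record which rule governed the children already ventilated (19 were randomized to VENT by the end of the 2021 season).

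If the HPS electrolyte schedule is tidied at the same time, first choose between 3-hourly checks for 24 hours (Section 4) and for 12 hours (Section 6.3). Sections 8.1 and 8.2.1 state a 6-hourly schedule from admission and would then follow.

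The cost is a wording amendment and a short record of the withdrawal rule used. No patients are added. Only the optional schedule change could add blood tests relative to 8.1 and 8.2.1.
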